**Table 3. Study Variables, Data Sources and Time Frame of Measurements**

Variable	Reference	Source	Index Visit	Time Frame		
				1 month	3 months	6 months
Sociodemographics, clinical, treatment data	NA	Chart review	X			
Knowledge of prognosis, EOL care options	Balboni 	Interview	X	X	X	
Feasibility and acceptability of the intervention	Matlock  , Barry 	Interview	X	X	X	
Spirituality	Balboni  Pargament 	Interview	X			

Health Literacy	NA	Interview	X			
Intent to consider EOL care options	NA	Interview	X	X	X	X
Decisional conflict, quality of life	O'Connor  Cohen 	Interview	X	X	X	
Healthcare and EOL utilization	NA	Interview, chart	X	X	X	X

**D.5.4. Statistical Analysis Plan:** We will use descriptive statistics to characterize study participants and proportion of intervention elements and follow-up assessments completed. The specificity and positive predictive value of the e-EOL algorithm operating in real world practice will be assessed using methods described for Aim 1 with physician chart review as the criterion standard. Acceptability and feasibility process data will be tallied. The main decision making outcome will be *change in the stage of intent to discuss EOL care options* from baseline through all follow-up intervals. Movement to an adjacent stage is a 1 point change. We will assess several aspects of stage change based on the proportion of patients at each time interval showing: 1) *any* stage pro/regression, and 2) *full progression* to the action stage of discussion EOL care options. Mean and range of progression at each interval will also be reported. The proportions above and means for *persistent* change will also be defined as the difference between baseline and 6 months (or 3 months if no 6 month contact or patient deceased). We will similarly examine pre- and post-intervention changes over time in knowledge, attitudes, and beliefs about EOL care and prognosis, decisional conflict, and QOL using non-parametric tests among the intervention group versus controls. Pre-specified subgroup analyses will stratify change in outcomes by: condition, mistrust, and spirituality. To achieve sensitivity of around 50% (with 10% confidence intervals, e.g. CI: 40% to 60%) in the outpatient algorithm, we will need to review 150 charts of patients diagnosed with metastatic (Stage III or IV) breast, lung and colorectal cancer (75 “test positive” and 75 “test negative” cases). The controlled pilot study in Aim 3 is designed to establish: feasibility, acceptability, detect preliminary efficacy signals (changes in behavioral intent, knowledge, attitudes, beliefs, decisional conflict), and generate point/variance estimates to be used to in power calculations for a future fully-powered RCT. We propose a small pilot RCT that will include 24 patient-caregiver pairs in each arm (intervention versus a usual care control group). This will yield greater than 80% power to detect a large intervention effect defined as an absolute difference in desired primary outcome of 40% (across a range of different point estimates), and between 60-70% power to detect a more modest absolute difference of 30% between the two groups (across a range of point estimates). To ensure the ability to recruit the additional patient-caregiver pairs for the study, we will extend the enrollment period from 15 months to 18 months. Parkland Hospital providers care for more than 900 breast, lung and colon cancer patients per year, and roughly 40% are African American; consequently we believe that we will able to successfully enroll this number of participants within our 18 month timeframe.

**D.5.5. Future Steps:** These results will provide the foundation for a R01 application to conduct a fully-powered study that will randomize AA patients with advanced cancer to the multi-component EOL counseling intervention vs. usual care. If a preliminary efficacy signal is absent, or feasibility problematic, will we first pursue a R21 grant to further refine and pilot the intervention. Other next steps would include adapting and testing a bilingual version of the intervention for Hispanics with advanced cancer, as well as testing the DVD and counseling intervention in the community setting. The e-EOL algorithm will also facilitate systematic identification of patients eligible for EOL care counseling for future audits of the quality and appropriateness of care for patients with advanced illness.

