**D.5.1. Study Subject Identification and Enrollment:** We will use the refined e-EOL algorithm in real-time to identify AA patients with Stage III or IV breast, lung, colorectal, prostate, or other advanced cancer for EOL care counseling. The e-EOL algorithm will run once every day to flag potentially eligible candidates using an IT protocol used successfully in previous intervention research at Parkland. The eligibility criteria are the same as those outlined in D.4.1. (AAs,  $\geq 21$  years, with advanced breast, lung or colon cancer, are English proficient, competent, cognitively intact by Mini-cog test, and no prior palliative care consult or receiving palliative care). Patients with earlier stage cancers (I and II) may be chosen for the intervention based on co-morbidities, functional status, or other factors that we deem appropriate. The research assistant will contact the patients' physicians to confirm eligibility and get permission to introduce the study to the patient. Once eligibility is confirmed, the research assistant will introduce the study to the patient, obtain informed consent, and administer the pre-intervention survey and needs assessment (described below). Each patient will be asked to identify a primary caregiver that will be able to participate in the intervention. Caregivers must be: 1) identified by the selected patient, 2)  $\geq 21$  years of age, 3) English proficient, and 4) competent to participate. The research assistant will then notify the EOL LHA of any study participants. The EOL LHA will contact each patient's primary caregiver by phone to confirm their participation in the study, and arrange a time to meet with both the patient and caregiver to conduct the intervention. We will recruit up to 60 patients and their caregivers, if a caregiver is available to participate, to allow us to pilot the intervention and sort out logistics of administering the intervention in a clinical setting prior to randomization. Overall, at least 48 patient-caregiver pairs will be randomized in the study representing an approximately even distribution across different cancer diagnoses. Twenty-four patient-caregiver pairs will be randomized to the intervention arm of the study, and twenty-four will be randomized to the usual care control group.

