Acceptability will be measured with Likert scale items rating “understandability, informativeness, balance, right amount of information, helpfulness, and “recommending this to others” used in published trials of decision aids. We will also ask open-ended questions on things they did or did not like about the intervention. The primary decision making outcome is change in intent to discuss EOL care options based on the Transtheoretical Stages of Change Model, an approach used in many other realms. We will categorize patients into the following stages: 1) Pre-contemplation: is unaware of EOL care options/has not thought about discussing this with a provider; 2) Contemplation: is aware of EOL care options/thinking about discussing options; 3) Preparation: intends to discuss EOL care issues with the doctor/has a plan for talking about it; 4) Action: has a discussion with the provider about EOL care. The completion stage is not applicable in this medical situation because the goal of the intervention is for the patient to have an informed discussion about benefits and harms of all treatment options including EOL care. The intent is NOT to get all patients to choose palliative care or hospice, or complete and an advance directive, but for them to understand how palliative care may benefit them now or in the future, and how it can be combined with curative care. *The goal is for the patient to make “the right decision for them” based on knowing all of the facts and options.*

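### Patients who have already discussed EOL care with a provider can enter at the top stage, cannot progress, and stay in the denominator of the progression proportions

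*Combined protocol and SAP*

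**What the plan says.** - **Entry (D.5.1).** Patients must be "competent, cognitively intact by Mini-cog test, and no prior palliative care consult or receiving palliative care". No criterion concerns an earlier EOL discussion with another provider, or the patient's stage. D.5.1 says its criteria are those of D.4.1, but D.4.1 lists criteria for provider focus groups and adds nothing here. The research assistant contacts the patients' "physicians to confirm eligibility and get permission to introduce the study to the patient"; this step carries no instruction to screen out earlier discussions.
- **Scale (D.5.3).** The top stage is "4) Action: has a discussion with the provider about EOL care". No time window is attached. Nothing lies above it: "The completion stage is not applicable in this medical situation".
- **Scope of the discussion (Aim 1).** EOL care options are defined to include advance care planning, so a talk about advance directives may qualify.
- **Timing (Table 3).** The item "Intent to consider EOL care options" is collected at the index visit and at 1, 3 and 6 months.
- **Analysis (D.5.4).** The main decision-making outcome is change in stage from baseline, with one point per adjacent stage. Proportions of patients are reported for any progression or regression and for full progression "to the action stage of discussion EOL care options". D.5.4 gives no rule for patients at Action at baseline, does not limit the denominator to those able to progress, and does not adjust for baseline stage.

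**The concern.** A patient whose oncologist or primary care doctor has already raised advance directives or hospice meets the entry criteria and sits at stage 4 on the first interview. That patient has no room to move up in either arm, so carries no information about whether the intervention promotes progression, but still counts in the denominator.

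The case is plausible. D.5.3 collects advance directive status as a variable that differs between patients. The outpatient algorithm in D.3 uses ED visits, hospitalizations and ICU stays, where such talks may occur. The preliminary studies in D.1 place the gap in care among patients who have not yet had an informed discussion, but neither the entry criteria nor the analysis confines the progression outcome to them.

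Two uses of the result are at stake. D.5.4 wants point and variance estimates for sizing a later trial, and D.5.5 makes the choice between an R01 and an R21 depend partly on whether an efficacy signal appears.

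**Working it through.** **Inputs from the plan (D.5.4):** 24 patient-caregiver pairs per arm; more than 80% power for a 40-point difference; 60-70% power for a 30-point difference.

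**Assumptions, because the plan gives none of these:** two-sided 5% test of two proportions; control rate 20% for the illustration; share f of each arm at Action at baseline of 5%, 10%, 20% or 30%.

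**Step 1. Reproduce the plan's figures.** With the pooled normal approximation and 24 per arm:
- A 40-point difference gives 81% to 96% power over control rates of 5% to 60%. The stated figure of more than 80% reproduces.
- A 30-point difference gives 68%, 63% and 59% at control rates of 10%, 15% and 20%, and 55-57% at 25-40%. The stated range holds for part of the range of control rates.

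Neither calculation allows for patients at the ceiling. For 20% vs 60%, exact enumeration of the pooled z-test gives 84% (normal approximation 83%). Exact values are used below.

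**Step 2. Keep ceiling patients as non-progressors.** If p is the progression rate among patients below Action, the rate over all patients is p × (1 − f), so a 40-point difference becomes 0.40 × (1 − f).

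**Step 3. Restrict to patients below Action at baseline.** The difference stays at 40 points, with about 24 × (1 − f) per arm: 21.6, 19.2 and 16.8 for f = 10%, 20% and 30%. Power was enumerated at 22, 19 and 17 per arm, and again with the number below Action varying by chance.

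| f | Rates over all 24 per arm | Difference | Power, all 24 | Power, restricted (fixed n / n varying) |
|---|---|---|---|---|
| 0 | 20% vs 60% | 40 | 84% | 84% |
| 10% | 18% vs 54% | 36 | 77% | 79% / 79% |
| 20% | 16% vs 48% | 32 | 69% | 76% / 74% |
| 30% | 14% vs 42% | 28 | 60% | 70% / 69% |

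The gain from restricting is about 2 points at a 10% share, 6 to 7 at 20% and 8 to 9 at 30%. At 5%, power is 81% either way and the gain is under 1 point.

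**The case against.** **The entry criteria already screen out some of these patients.** This stands in part. A prior palliative care consult is likely to have included such a discussion, and the outpatient algorithm aims at patients early in advanced disease. The share at Action may be small, and nothing in the documents supports 20% or 30% in particular. It would be wrong to infer that entry offers no protection at all.

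**The 40 points may be meant over everyone randomised.** D.5.4 does state the difference between arms of 24. On that reading no power is lost against the plan's own figure. The effect needed among patients able to progress is then larger: 0.40 / (1 − f), or 44, 50 and 57 points at f = 10%, 20% and 30%.

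**The all-patient difference may be the right input for the later trial.** This stands if that trial keeps the same entry criteria. An estimate from patients below Action alone would then be too large and would undersize it. Both figures are needed.

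**Stronger readings that the documents do not support.**
- A reader might infer that patients already at Action would be counted as responders, inflating the rate in both arms. D.5.4 presents full progression as an aspect of change from baseline, and a patient at stage 4 both times has changed by zero. Counting that patient is an unlikely reading, though one sentence would rule it out.
- A reader might infer that the comparison is biased. Randomisation balances these patients on average; chance imbalance is possible at 24 per arm.
- A reader might want Action held once reached, since a discussion cannot be undone. D.5.4 deliberately reports regression and persistent change, and such a rule would conflict with that.

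**Conclusion.** The point holds as a modest, correctable weakness in how two proportions are defined. The ceiling follows directly from the four-stage scale and the entry criteria. That the affected patients stay in the denominator is the plain reading of D.5.4, which is silent rather than explicit. Each 10% of patients at Action at baseline takes 4 points off a true 40-point difference. The power loss, and the part that restriction recovers, rest on an unknown baseline share, an assumed 20% control rate and a two-sided 5% test. At shares of 5% to 10% the practical gain is small; at 20% to 30% it is worth having. This is a pilot whose main process outcomes are feasibility and acceptability, so the chief harm is to the interpretation of the efficacy signal and of the estimates passed to the next trial.

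**What to change.** In D.5.4:
1. Calculate any progression and full progression to Action among patients below Action at the index visit. The stage is already collected there, and D.5.1 places the pre-intervention survey at consent. State that this interview precedes randomisation, so that the subset is defined before allocation.
2. Report the number at Action at baseline by arm.
3. Give the same two proportions over all randomised patients alongside, for sizing a later trial with the same entry criteria.
4. State that a patient at Action at both baseline and follow-up is not a full progression.

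The cost is a few sentences in the analysis plan. There are no added patients, visits or interview items. The drawback is a somewhat smaller denominator for the two restricted proportions: about 22, 19 or 17 per arm at shares of 10%, 20% or 30%.

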### D. APPROACH

#### D.1 PRELIMINARY STUDIES

Several pilot studies provide a solid foundation for the proposed research. To establish the feasibility of using EMR data to identify patients with advanced cancer, we have developed a preliminary electronic (e-EOL) algorithm adapting applied medical informatics approaches that [name] and others at UTSW have successfully used in prior studies. To date, a prototype *inpatient* e-EOL algorithm has been piloted for patients with advanced lung and breast cancer based on the ICD-9 codes displayed in Table 1. A total of 369 breast and lung cancer patients were hospitalized at Parkland Hospital from 2009 – 2010. Of those, 14% were flagged by the algorithm as meeting national guideline criteria as most appropriate for an in-depth discussion about EOL care options. Of those identified, 39% had breast cancer and 58% had lung cancer. The e-EOL algorithm identified 53 (14%) patients that met assigned criteria (presence of metastatic disease and albumin < 2.5 g/dl), while physician chart abstractors felt that 64% of patients met criteria indicating a need for in-depth discussion about EOL care options. Over half (55%) of those identified by the e-EOL algorithm were African American (19% were white, and 25% Hispanic). When compared to physician chart review (the criterion gold standard), the sensitivity, specificity, and positive predictive value (PPV) of the pilot algorithm were as follows: 21% (95% CI: 16% to 26%), 96% (95% CI: 93% to 100%), and 91% (95% CI: 83% to 98%) respectively. Thus, this preliminary e-EOL algorithm had very good specificity and PPV and identified many AA inpatients with advanced breast and lung cancer. Additionally, construct validity in the form of survival analysis revealed that patients meeting e-EOL algorithm criteria ("test positive" cases) had worsened survival compared to those

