National guidelines that aid health care providers in determining a patient's eligibility for hospice and EOL option discussions are available, and several national organizations recommend guidelines for the institution of palliative care. The *inpatient* e-EOL algorithm operationalizes the application of hospice guidelines and clinical experience by ‘flagging’ those individuals with advanced cancer meeting guideline criteria for hospice eligibility; however, the *outpatient* e-EOL algorithm will target patients who are earlier in the cancer disease trajectory and would benefit from early palliative care consultation. The preliminary *inpatient* e-EOL algorithm was based on simple ICD-9 codes from the index admission (cancer, metastasis) and albumin measurements; however, UTSW, Parkland and all of their affiliated clinics adopted ICD-10 on October 1, 2015, and the algorithm is now being tested using these updated codes. The *outpatient* algorithm will harness a broadened range of factors contained in discreet fields from the EMR including: patient characteristics (age, race), initial determination of metastatic cancer diagnosis (stage III or IV disease), medications to treat pain and other cancer-related symptoms (opioids/NSAIDs/steroids, anti-emetics, appetite stimulants, antidepressants), processes of care (chemotherapy, radiation therapy), as well as number of ED visits, hospitalizations and ICU stays related to the primary cancer diagnosis. *Albumin < 2.5 mg/dl will not be used in this algorithm as it is a marker of poor prognosis, and we hope to detect patients with metastatic disease earlier in their disease trajectory.* We will explore the impact of different types of Boolean logic combining these factors. We will also broaden our net to include ICD-10 codes in diagnosis, problem lists, and encounter fields of all prior inpatient and outpatient encounters in the past 12 months. Our goal is to increase have sensitivity of the inpatient algorithm of 40-50% and specificity of >90%.

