and “negative” cases to help them develop a shared understanding. Once the training is completed, two reviewers will independently review the EMR for each case and render a final judgment about whether the patient: 1) has Stage III/IV breast, lung, colon, prostate or other advanced cancer, and 2) meets guideline criteria for being eligible for an EOL care options discussion. Initial agreement and Kappa scores will be computed, and areas of disagreement will be resolved by discussion. The third reviewer will be used if consensus cannot be reached. Sensitivity, specificity, and positive/negative predictive values for the algorithm will be calculated. The e-EOL algorithm results define “test positivity” and physician chart review as the criterion standard (denominator). The e-EOL algorithm will be iteratively refined to improve its test operating characteristics. For the purposes of this project, assuring adequate specificity (80-90%) will be more important than optimal sensitivity (40-50%).

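### Aim 1 samples 75 flagged and 75 unflagged charts but does not weight back to the true flag counts, so sensitivity computed directly averages above 50% for any useful algorithm

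*Combined protocol and SAP*

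**What the plan says.** Section D.5.4 sets the size of the chart review by precision: "To achieve sensitivity of around 50% (with 10% confidence intervals, e.g. CI: 40% to 60". It puts the requirement at 150 charts and splits them by algorithm result: "breast, lung and colorectal cancer (75 “test positive” and 75 “test negative” cases".

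Section D.3 says that sensitivity, specificity and predictive values will be calculated, with "physician chart review as the criterion standard (denominator". The stated priority is that "assuring adequate specificity (80-90%) will be more important than optimal sensitivity (40-50" percent. The results feed back into the algorithm: "The e-EOL algorithm will be iteratively refined to improve its test operating characteristics". Several candidate rules are expected: "We will explore the impact of different types of Boolean logic combining these factors".

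The plan does not give the flagged and unflagged totals from which the charts are drawn, the sampling fractions, the method of drawing them, or any weighting.

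**The concern.** Sensitivity is the share of criterion-positive patients whom the algorithm flags. It can be read directly from a sample only if flagged and unflagged patients appear at their natural rates. Here the rates are fixed at 1:1 by design. If the algorithm naturally flags fewer than half, flagged charts are over-represented, so sensitivity reads too high and specificity too low. If it flags more than half, both biases reverse.

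A natural rate of 50% does not fit the plan. In the inpatient pilot, "The e-EOL algorithm identified 53 (14%) patients that met assigned criteria". With sensitivity at most 50% and specificity at least 80%, the flag rate is at most 0.5p + 0.2(1 − p), where p is prevalence, and this is below 50% for every p below 1. Some of the Boolean combinations explored could flag more.

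These figures are the Aim 1 result and steer the refinement. A rule with weak sensitivity could appear to meet the goal. A rule that meets the specificity goal, which the plan ranks first, could appear to miss it and be tightened without need.

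**Working it through.** **Inputs.** 75 flagged and 75 unflagged charts, target sensitivity 50% ± 10 points (D.5.4). Goals of sensitivity 40-50% and specificity 80-90% (D.3). Pilot: 369 patients, 53 flagged, sensitivity 21%, specificity 96%, PPV 91%, and "physician chart abstractors felt that 64% of patients met criteria" (D.1). Outpatient prevalence is not given. I use 64% as the only documented value and vary it by assumption.

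**The plan's 150.** 1.96² × 0.5 × 0.5 / 0.10² = 96.04 criterion-positive charts, and 96.04 / 0.64 = 150.06. The plan does not state the division by 0.64; I infer it because it reproduces the figure. It presumes an unselected sample, which a fixed 75/75 split is not. The bias below does not depend on this inference.

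**Formulas.** For prevalence p, sensitivity Se and specificity Sp:
- flag rate f = p·Se + (1 − p)(1 − Sp)
- PPV = p·Se / f
- 1 − NPV = p(1 − Se) / (1 − f)
- expected unweighted sensitivity at 75/75 ≈ PPV / (PPV + 1 − NPV)
- expected unweighted specificity at 75/75 ≈ NPV / (NPV + 1 − PPV)

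The sensitivity expression exceeds 50% exactly when PPV > 1 − NPV, which is the same as Se + Sp > 1.

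**Worked case: p = 0.64, Se = 0.50, Sp = 0.90.**
- f = 0.320 + 0.036 = 0.356
- PPV = 0.320 / 0.356 = 0.899
- 1 − NPV = 0.320 / 0.644 = 0.497
- sensitivity reads 0.899 / (0.899 + 0.497) = 64%
- specificity reads 0.503 / (0.503 + 0.101) = 83%

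About 75 × (0.899 + 0.497) = 104.7 charts are criterion-positive. The unweighted interval is therefore about ±9 points, close to the planned width but centred on 64%.

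**Other cases (sensitivity / specificity).**

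| Prevalence | True | Unweighted reading |
|---|---|---|
| 64% | 50% / 80% | 61% / 72% |
| 64% | 40% / 90% | 62% / 79% |
| 64% | 30% / 90% | 59% / 73% |
| 90% (assumed) | 50% / 90% | 54% / 88% |
| 80% (assumed) | 50% / 90% | 58% / 87% |
| 50% (assumed) | 50% / 90% | 70% / 79% |
| 30% (assumed) | 50% / 90% | 78% / 72% |
| 90% (assumed) | 30% / 90% | 52% / 78% |

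Reversal: at 64% prevalence a 70% / 70% rule flags 56% and reads 65% / 75%.

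**Pilot as illustration.** The pilot figures are consistent with 48 true positives, 5 false positives, 188 false negatives and 128 true negatives: sensitivity 48/236 = 20%, specificity 128/133 = 96%, PPV 48/53 = 91%. At 75/75 this gives 75 × 48/53 = 67.9 true positives and 75 × 188/316 = 44.6 false negatives. Sensitivity reads 67.9/112.5 = 60%, and specificity 81%.

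**Simulation (200,000 samples per case).**
- 50% / 90% at 64% prevalence: the unweighted 95% interval covers the true 50% in about 2.5% of samples. Specificity reads below 80% in about 24%, against 0.3% when weighted.
- 50% / 80% at 64%: coverage is 33%. Specificity reads below 80% in 92%, against 49% when weighted.
- 50% / 90% at 80% and 90% prevalence: coverage is 65% and 99.8%.
- Weighting recovers 50% / 90% on average.

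**Precision when weighted.** Half-width for sensitivity = 1.96·Se(1 − Se)·√[(1 − PPV)/(75·PPV) + NPV/(75(1 − NPV))]. For 50% / 90% this is about 6, 8, 10 and 12 points at prevalences of 64%, 50%, 39% and 30%. At 30%, ±10 points needs 150 × (0.1222/0.10)² ≈ 224 charts.

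**The case against.** The plan says only that the measures will be calculated. It does not commit to an unweighted estimator, and the same 150 charts give valid answers once two counts are added, so this could be called an unstated detail. That is true of the design: the charts can be kept. It does not rescue the text. The only stated computation uses chart review as the denominator, with no flag totals or weights, and following it gives the biased result.

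Section D.3 also says that, as in the pilot, each test-positive and test-negative case will be reviewed. The pilot figures fit complete review of all 369 patients, where direct calculation is valid. This makes the intended sample less clear, but it does not remove the explicit 75/75 split in D.5.4.

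The 64% comes from hospitalised breast and lung cancer patients. The Aim 1 charts are outpatients with Stage III or IV disease, including colorectal cancer, and their prevalence could be higher or lower. This objection stands as a limit on size. The low coverage of 2.5% belongs to one scenario, and for the 50% / 90% rule the bias is small at 90% prevalence. That is not general: the 30% / 90% rule at 90% prevalence still reads 52% / 78%.

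The consequences are bounded. Physicians confirm eligibility before enrolment (D.5.1), and sensitivity is ranked below specificity. But specificity is biased too, so the ranking does not protect the result.

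**Conclusion.** The concern holds and should be fixed. As written, the Aim 1 sensitivity has an expected value above 50% for any algorithm better than chance, so it cannot be judged against a 40-50% goal. At 64% prevalence the upward bias is 14 points for a 50% / 90% rule (64 − 50) and 29 points for a 30% / 90% rule (59 − 30). Specificity reads 7 and 17 points too low (90 − 83 and 90 − 73). The existence of the bias rests only on the 75/75 split and direct calculation. Its size rests on outpatient prevalence, which is unknown, and its direction on the rule flagging fewer than half, which holds at the plan's goals.

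The harm is confined to reporting and tuning the algorithm. PPV and NPV of the sampled version are unaffected if charts are drawn at random within each flag group, and so is the randomised comparison. Aim 3 specificity is affected only if charts there are also sampled by test result, which the plan does not say.

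**What to change.** Keep the 150 charts and amend D.3 and D.5.4 as follows.

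- Draw the charts at random within each flag group, and record the total flagged and unflagged in the sampling frame.
- Report sensitivity and specificity weighted by those totals, with a stratified (delta-method or bootstrap) confidence interval. Report PPV and NPV directly.
- State the prevalence assumed for the precision claim, since the weighted half-width for sensitivity depends on it. At very high prevalence specificity becomes the weak measure: at 90%, only about 14 charts are criterion-negative.
- If a refined rule is evaluated on the same charts, keep the original sampling weights for all its measures, including PPV and NPV, and label that performance as apparent.
- Use the same estimator for Aim 3 specificity only if charts there are also sampled by test result.

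The cost is SAP wording, a random draw and two counts from the EMR run. No extra charts are needed for ±10 points on sensitivity if prevalence is about 39% or more; at 30% about 224 would be needed. An unbiased test of a refined rule would need separate charts.
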